4.1.7 Kaplan-Meier curve and estimates for time-to-event analyses

Kaplan-Meier plots (Kaplan and Meier 1958) of time to event variables will be displayed by treatment group. Unless otherwise specified, the plot will be presented only when there are at least 5 events in one treatment group. Additionally, a table will accompany the plot and will display the Kaplan-Meier estimates of the cumulative proportion (with 95% CI calculated based on Greenwood's method when applicable) (Greenwood 1926) of subjects with event at

specific time points by treatment group. If the estimated lower bound of 95% CI is below 0 or the estimated upper bound of 95% CI is over 1, then it will be restricted to 0 or 1 respectively.

4.1.8 Proportion of subjects with a pre-defined characteristic at week t

The proportion of subjects with a pre-defined characteristic at Week t will be analyzed using a logistic regression model with adjustments for baseline values and randomization strata when there are at least 5 responders on average by treatment group. This pre-defined characteristic could correspond to a continuous variable dichotomized into a categorical endpoint. The odds ratio in response rate between each of the dapagliflozin treatment groups and the control group will be displayed along with the 2-sided 95% confidence intervals. P-values will be calculated if applicable. When there are less than 5 responders on average by treatment group, the unadjusted (and difference) proportions, exact 95% confidence interval, and p-values from the Fisher's exact test (when applicable) will be provided.

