1.2 Study design

[figure not shown]
This trial is a randomized, double-blinded, three-arm, parallel-group, placebo-controlled, multicenter trial to evaluate the efficacy and safety of dapagliflozin, when added to ongoing insulin therapy, in subjects with T1DM and inadequate glycemic control.

Potential subjects will be assessed for eligibility criteria at the screening visit. Eligible subjects will enter an 8-week lead-in period in order to optimize their diabetes management based on individual subject challenge to glycemic control (including hyperglycemia, hypoglycemia, erratic meal/exercise patterns, as defined by the investigator) and to assess the variability in blood glucose profiles and frequency of hypoglycemic episodes at baseline. No placebo or study medication will be provided during the lead-in period. On the Day 1 visit, subjects who meet all the protocol-specific enrollment and randomization criteria will be randomized into one of the three blinded treatment arms (dapagliflozin 5 mg QD, dapagliflozin 10 mg QD, or placebo QD) in a 1:1:1 ratio. Randomization will be stratified by the following factors to ensure equal representation across all treatment groups: 1) current use of CGM (this refers to an unblinded/personal device which may already be in use before using the blinded device as part of the study) categorized as yes vs. no; 2) method of insulin administration at baseline (multiple daily injections (MDI) three or more injections per day vs. continuous subcutaneous insulin infusion - CSII); and 3) baseline A1C $\geq 7.5\%$ and $< 9.0\%$ vs. $\geq 9.0\%$ and $\leq 10.5\%$.

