1.3 Number of subjects

The primary endpoint is the change from baseline in HbA1c to Week 24 visit.

With 243 subjects per treatment group with both baseline and at least one post baseline measurement, there is approximately 90% power to detect a difference in means of 0.35% between each dapagliflozin treatment group and placebo at the two-sided 0.0262 significance level (based on Dunnett and Tamhane step-up procedure) (Dunnett and Tamhane 1992), assuming a standard deviation (SD) of 1.1%. Assuming that 5% of subjects do not have a post-baseline assessment, a total of 768 subjects (256 subjects per treatment arm) need to be randomized to each dapagliflozin or placebo group in 1:1:1 ratio. Due to regulatory requirements, approximately 160 subjects from Japan will be included (of the total population of 768 subjects).

A mean reduction in the primary endpoint of change from baseline in HbA1c of 0.35% was used to determine sample size as this represents a clinically meaningful improvement in glycemic control under the current study design with adjustable background insulin dose. A lesser degree of reduction in HbA1c in combination with other beneficial outcomes in secondary endpoints may also be clinically important.

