The analysis of the change in each of the CGM parameters from baseline to Week 24 will be based on a longitudinal repeated measures analysis using ‘direct likelihood’ as outlined in Section 4.1.6.2.

The model will use subjects in the primary efficacy dataset (i.e., Full Analysis Set) who have at least one baseline assessment and any post-baseline double-blind treatment period assessment.

Point estimates and 2-sided 95% confidence intervals for the mean change within each treatment group, as well as the difference in mean change between each dapagliflozin treatment group and placebo, will be calculated. Only for the secondary endpoints, t-statistic corresponding to the Type III sums of squares for the differences in the least squares means

between each dapagliflozin group and placebo at Week 24 will be calculated. No p-value will be estimated for the exploratory analyses.

Proportion of subjects achieving glycemic response

The proportion of subjects having an HbA1c reduction from baseline to Week 24 (LOCF) \geq 0.5% and without severe hypoglycemia events is a secondary combined endpoint.

The proportion will be analyzed using the methodology outlined in Section 4.1.8. The odds ratio and its 2-sided 95% confidence interval between each dapagliflozin treatment group and placebo, will be calculated. The analysis will use subjects in the primary efficacy dataset (i.e., Full Analysis Set) who have at least one baseline assessment and any post-baseline double-blind treatment period assessment.

The proportion of subjects having an HbA1c reduction from baseline to Week 24 LOCF \geq 0.5% and an HbA1c Week 24 LOCF value $<$ 7% are separate exploratory endpoints; therefore no statistical testing will be performed to compare each dapagliflozin group and placebo.

Number of non-severe hypoglycemic events per subject in those achieving a HbA1c reduction of \geq 0.5% from baseline to the week 24 visit (LOCF) is an exploratory endpoint; therefore no statistical testing will be performed to compare each dapagliflozin group and placebo.

Analyses will be analyzed using the methodology outlined in Section 4.1.8 using the randomized subjects dataset and the LOCF visit. No p-value will be calculated. The analysis will use subjects in the primary efficacy dataset (i.e., Full Analysis Set) who have at least one baseline assessment and any post-baseline double-blind treatment period assessment.

Change from baseline in fasting plasma glucose

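### Minor: the sparse-data switch in SAP 4.1.8 uses the average responder count over arms, so a comparison with an empty arm can be sent to a logistic model that has no finite odds ratio

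*SAP*

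**What the plan says.** SAP section 4.1.8 covers any yes/no characteristic at a given week. It specifies a "logistic regression model with adjustments for baseline values and randomization strata when there are at least 5 responders on average by treatment group". Its output is pairwise: "The odds ratio in response rate between each of the dapagliflozin treatment groups and the control group will be displayed", each with a two-sided 95% interval. The type of interval is not named. The other branch reads: "When there are less than 5 responders on average by treatment group, the unadjusted (and difference) proportions, exact 95% confidence interval", plus Fisher p-values where applicable.

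Section 4.2.3.2 sends two kinds of endpoint to this method. One is the sixth secondary endpoint (HbA1c reduction of at least 0.5% with no severe hypoglycemia), which is formally tested. The others are exploratory, among them HbA1c below 7% at Week 24: "Analyses will be analyzed using the methodology outlined in Section 4.1.8". For these the SAP rules out p-values.

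The trial has three equal arms (section 1.2: "dapagliflozin 5 mg QD, dapagliflozin 10 mg QD, or placebo QD) in a 1:1:1 ratio"). Section 4.1.6.1 gives ordered back-up models in case the mixed model does not converge. Section 4.1.8 has nothing comparable for the logistic model.

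**The concern.** The switch exists to keep sparse data out of an ordinary logistic model, but it looks at the wrong quantity. An average over three arms sets no minimum for the two arms being compared. One empty arm can be masked by responders in the other two. Maximum likelihood then has no finite solution for a comparison that involves the empty arm, and what the software prints depends on where its iterations stop.

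At stake is the legibility of an odds ratio and its interval. For the exploratory proportions these are the whole comparative result. A repair chosen after unblinding would be a data-driven change of method.

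**Working it through.** **Inputs.** Three arms, 1:1:1 (section 1.2). Section 1.3: "With 243 subjects per treatment group with both baseline and at least one post baseline measurement", difference 0.35, SD 1.1, two-sided level 0.0262, power 90%. The SAP gives no responder rates, so any rate below is an assumption.

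**The SAP's own figure.** n per arm = 2 × (2.223 + 1.282)² × 1.1² / 0.35² = 2 × 12.29 × 1.21 / 0.1225 ≈ 242.7, rounded up to 243. It reproduces, so 243 per arm is used throughout.

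**The rule as arithmetic.** An average of at least 5 over 3 arms means a total of at least 15. A total of 14 or fewer goes to the exact branch.

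**Routing and result** (placebo / 5 mg / 10 mg, each out of 243; maximum-likelihood logistic fit; Fisher's exact test on the same pair for reference):

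| Counts | Average | Branch | Result |
|---|---|---|---|
| 0/7/7 | 4.67 | exact | Fisher p = 0.015 for each comparison |
| 0/8/8 | 5.33 | logistic | log odds ratio 6.2 (SE 4.7) after 8 iterations, 23.2 (SE about 22,800) after 25; Wald p then 0.999; Fisher p = 0.0074 |
| 8/0/8 | 5.33 | logistic | 5 mg log odds ratio about −23, so odds ratio tends to 0; 10 mg comparison intact: 1.0 (0.37 to 2.71) |
| 0/0/15 | 5.00 | logistic | 10 mg comparison diverges; Fisher p = 0.00005 |

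For 0/8/8 after 25 iterations the Wald limits on the log scale are 23.2 ± 1.96 × 22,800, so the interval runs from effectively zero to infinity. Adding a baseline covariate and eight simulated strata does not change this. Going from 0/7/7 to 0/8/8 strengthens the evidence but moves the analysis from a valid exact result to one with no finite estimate.

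**Is this likely for the tested endpoint?** Assume normal changes with SD 1.1 and no mean change on placebo, and ignore the hypoglycemia component. The response rate is Φ(−0.5/1.1) ≈ 0.325, or about 79 of 243. The chance of an empty arm is (1 − 0.325)^243, about 4 × 10⁻⁴². With a mean worsening of 0.5% on placebo the rate is Φ(−1.0/1.1) ≈ 0.18, and the chance is about 7 × 10⁻²².

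**Is it likely for HbA1c below 7%?** Assume baseline uniform on 7.5% to 10.5% (the stratum limits) and normal changes. The rate is the average of Φ((7 − baseline − worsening)/SD) over that range.

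- SD 1.1, no mean change: rate about 7.8%, 19 expected responders. The chance of an empty arm is about 3 × 10⁻⁹, and of fewer than 5 responders about 0.003%.
- SD 1.1, worsening 0.3%: rate about 5.0%. The chance of an empty arm is about 4 × 10⁻⁶.
- SD 0.7, worsening 0.2%: rate about 1.9%, 4.7 expected. The chance of an empty arm is (1 − 0.0194)^243, about 0.8%, and of fewer than 5 responders about 49%.

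**The case against.** The strongest reply is that this is a remote corner case. The SAP already has a sparse-data fallback, the tested endpoint will have dozens of responders per arm, and the exploratory endpoints carry no test. Most of that stands and limits the point to a minor one. What remains is that the fallback is triggered by a quantity that does not describe the comparison being reported.

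A reader might infer more, in four ways that the SAP does not support:

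- **That any empty arm breaks the analysis.** With 14 or fewer responders in total, the exact branch applies.
- **That the odds ratio is always infinite.** It diverges upward only if placebo is empty, and then for each dapagliflozin arm that has responders. An empty dapagliflozin arm sends its own odds ratio to 0 and leaves the other comparison estimable.
- **That a true effect would be declared non-significant.** For HbA1c below 7% no p-value is planned, so none can be wrong. For the tested endpoint the situation will not realistically arise.
- **That no logistic inference could survive.** The failure is of Wald inference, and the SAP names no interval type. For 0 against 8 of 243, the likelihood-ratio p-value from the same model is 0.0008, and the profile-likelihood lower limit for the odds ratio is about 3.8. The upper limit remains unbounded.

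Nor can one fixed probability be put on an empty arm, because the SAP states no rates. The number of model terms is also open: section 4.1.8 does not say whether strata enter as combinations or as separate factors.

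**Conclusion.** The point holds as a minor specification error. The threshold in section 4.1.8 is set on the total over three arms, while the estimates are pairwise. When one arm is empty and the total is at least 15, the planned odds ratio does not exist and a Wald interval says nothing. That part is arithmetic and needs no assumed rate.

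Its practical reach is small. It does not threaten the sixth secondary endpoint. For HbA1c below 7% an empty placebo arm is unlikely (from about 3 × 10⁻⁹ to about 0.8% in the scenarios with SD 1.1 and no change, and SD 0.7 with 0.2% worsening). A placebo count below 5, where the estimate is finite but rests on very few events, ranges from about 0.003% to about 49% over the same two scenarios. These ranges rest on normal changes and a uniform baseline; the SD of 0.7 and the worsening are illustrative and are not in the SAP.

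**What to change.** Replace the averaging rule in section 4.1.8 with one set per comparison. Fit the ordinary logistic model only if both arms of the comparison have at least 5 responders and at least 5 non-responders. Otherwise use Firth penalised-likelihood logistic regression with profile-likelihood intervals, or the exact method already planned. Name the interval type for the main branch as well.

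Under this rule 5/5/5 stays with ordinary logistic regression. Both comparisons in 0/8/8 and 0/0/15 go to the fallback, as does the 5 mg comparison in 8/0/8. Firth gives a finite estimate in the empty-arm case. Without covariates it amounts to adding one half to each cell, so 0 against 8 of 243 gives (8.5/235.5) / (0.5/243.5) ≈ 17.6.

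The cost is a sentence or two before unblinding and a standard SAS option. Firth shrinks the estimate slightly toward no effect; choosing the exact method instead gives up the covariate adjustment.

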4.2 Analysis methods

4.2.1 Study population

4.2.1.1 Subject disposition

The disposition of subjects for the pre-randomization period and the short-term double-blind treatment period will be summarized.

The status in the pre-randomization period will be summarized based on all subjects enrolled (who signed informed consent). That includes all subjects who entered lead-in period, subjects who completed lead-in period, reasons for treatment discontinuation from lead-in period, subjects who were randomized, subjects who were not randomized, and reasons for not being randomized. The summary of status in the short-term double-blind treatment period will include all randomized subjects, and be presented by randomized treatment group. This summary will include subjects completing and discontinuing treatment during the short-term double-blind treatment period with reasons for treatment discontinuation from the short-term double-blind treatment period, and their status (completing the short-term treatment, continuing to long-term treatment, continuing to short-term off-treatment, long-term off-treatment and 30 day follow up) after double-blind treatment period. This summary will be repeated for Japanese subjects.

Subjects enrolled, randomized, and treated will be summarized by country and study site.

4.2.1.2 Demographic and other baseline characteristics

Demographic and other baseline characteristics, including diabetes-related characteristics and renal function characteristics will be summarized by treatment group and overall, using the Full Analysis Set and the Per Protocol Analysis Set if deemed necessary.

Demographic and baseline characteristics are listed in Table 4. Diabetes related baseline characteristics are listed in Table 5. Renal function baseline characteristics are listed in Table 6.

All summaries of continuous characteristics will be based on non-missing observations. For categorical characteristics, percentages will be calculated out of the total number of subjects in the data set, overall and by treatment group (i.e., each denominator includes the number of subjects with missing/unknown values for the characteristic). This summary will be repeated for Japanese subjects.

Table 4 Demographic and Baseline Characteristics

Characteristic	Summarized as	Categories
Gender	Categorical	Male, Female
Age	Categorical and Continuous	< 65yrs ≥ 65yrs and <75yrs ≥ 75yrs
Age	Categorical	<35yrs ≥35yrs and <50yrs ≥50yrs
Female Age	Categorical	≤ 50yrs > 50yrs
Race	Categorical	White, Black or African American, Asian, Other
Country	Categorical	Japan Other
Ethnicity	Categorical	Hispanic/Latino, Non Hispanic/Latino
Body Weight	Continuous	-
Body Mass Index	Categorical and Continuous	≤ 23kg/m ² > 23kg/m ² - ≤ 25kg/m ² > 25kg/m ² - ≤ 27kg/m ² > 27kg/m ² - ≤ 30kg/m ² > 30kg/m ²
Geographic Region	Categorical	As defined in Appendix 9.2

Table 5 Diabetes-Related Baseline Characteristics

Duration of Type 1 Diabetes	Categorical and Continuous	$< 10\text{yrs}$ $\geq 10 \text{ and } \leq 20\text{yrs}$ $> 20\text{yrs}$
HbA1c	Categorical and Continuous	$< 8\%$ $\geq 8 \text{ and } < 9\%$ $\geq 9\%$
FPG	Continuous	-
Fasting C-peptide	Continuous	-
Fasting C-peptide	Categorical	$< 0.05\text{ng/mL}$ (lower limit of detection) $\geq 0.05\text{ng/mL}$
Method of insulin administration	Categorical	Multiple Daily Injections Continuous Subcutaneous Insulin Infusion
Use of continuous glucose monitoring (CGM)	Categorical	Yes No
Baseline HbA1c	Categorical	$\geq 7.5\% \text{ and } < 9.0\%$ $\geq 9.0\% \text{ and } \leq 10.5\%$

Combinations of randomization stratification factors	Categorical	Baseline HbA1c $\geq 7.5\%$ and $< 9.0\%$ - Multiple Daily Injections - with CGM use
		Baseline HbA1c $\geq 7.5\%$ and $< 9.0\%$ - Multiple Daily Injections - without CGM use
		Baseline HbA1c $\geq 7.5\%$ and $< 9.0\%$ - Continuous Subcutaneous Insulin Infusion - with CGM use
		Baseline HbA1c $\geq 7.5\%$ and $< 9.0\%$ - Continuous Subcutaneous Insulin Infusion - without CGM use
		Baseline HbA1c $\geq 9.0\%$ and $\leq 10.5\%$ - Multiple Daily Injections - with CGM use
		Baseline HbA1c $\geq 9.0\%$ and $\leq 10.5\%$ - Multiple Daily Injections - without CGM use
		Baseline HbA1c $\geq 9.0\%$ and $\leq 10.5\%$ - Continuous Subcutaneous Insulin Infusion - with CGM use
		Baseline HbA1c $\geq 9.0\%$ and $\leq 10.5\%$ - Continuous Subcutaneous Insulin Infusion - without CGM use

Table 6 Baseline Renal Function Characteristics

Characteristic	Summarized as	Categories
eGFR (MDRD)	Categorical	$< 60\text{mL/min/1.73m}^2$ ≥ 60 and $< 90\text{mL/min/1.73m}^2$ $\geq 90\text{mL/min/1.73m}^2$
Calculated Creatinine Clearance using the Cockcroft and Gault method	Categorical	$< 60\text{mL/min}$ ≥ 60 and $< 90\text{mL/min}$ $\geq 90\text{mL/min}$

4.2.1.3 Specific and general disease histories

The number (percent) of subjects with type 1 diabetes, diabetes-related disease histories will be summarized by treatment group and overall using the Full Analysis Set.

The number (percent) of subjects with general medical history findings will also be summarized by treatment group and overall using the Full Analysis Set.

4.2.2 Extent of exposure

4.2.2.1 Study medication

The extent of exposure to double-blind study medication during the short-term double-blind treatment period is defined as the difference between the last and the first dose of study medication of the short-term double-blind treatment period plus 1 day. The extent of exposure to double-blind study medication will be summarized using the Treated Subjects data set for the short-term double-blind treatment period, where the number and percent of subjects with an extent of exposure within pre-specified day ranges will be presented by treatment group. The categorization for the short-term double-blind treatment period of 24 weeks is 1-7, 8-30, 31-60, 61-90, 91-120, 121-180, > 180 days. The mean (SD), median and range of the number of days of exposure will also be presented.

In addition, the exposure in terms of total patient-years will be calculated by treatment group using the sum of the exposure to study medication of all subjects (in years) in a treatment group.

4.2.2.2 Interruption of study medication

Interruption of study drug is indicated by 0 tablets of study medication recorded on the CRF.

4.2.2.3 Current and concomitant medications

Concomitant medications and current medications will be summarized using the Treated Subjects dataset by drug class and (generic) drug name. A summary table by drug class and generic drug name will be generated for each of the following:

- all concomitant medication
- all concomitant diuretic medication
- all concomitant loop diuretic medication
- all concomitant ARB and/or ACE-I medication
- all concomitant anti-hypertensive medication

Current medications are defined as medications with a start date prior to the first day of short-term double-blind treatment period and without a stop date prior to the consent date, i.e. current medication will be any medication with at least 1 dose taken on or after the day of consent date up to the day prior to the first dose of study medication.

Concomitant medication during the short-term double-blind treatment period is defined as a medication with either

- a recorded medication start date falling within the short-term double-blind treatment period, or

- a recorded medication start date prior to the first day of study medication during the short-term double-blind treatment period without any recorded medication stop date prior to the start of the short-term double-blind treatment period.

This means that concomitant medications for the short-term double-blind treatment period will be any medication taken from the start of the short-term double-blind treatment period up to the end of the short-term double-blind treatment period.

Missing and partial date handling of start and stop dates of previous, current and concomitant medications, is described in Section 6.6. The World Health Organization (WHO) dictionary is used to code non-study medications.

4.2.2.4 Measurements of treatment compliance

Percent treatment compliance is calculated during the short-term double-blind treatment period for each treatment group. For each subject, percent compliance is defined as the number of tablets taken divided by the number of tablets that should have been taken. A subject is considered compliant if percent compliance is $\geq 80\%$ and $\leq 120\%$. The number and percent of subjects compliant during the short-term double-blind treatment period will be displayed for the Safety Analysis Set by treatment group.

Compliance will be calculated for the double-blind study medication (dapagliflozin or placebo, respectively).

Details in calculating percent compliance are specified in Section 6.9.

